#### Screening

The investigator should determine the clinical significance of any abnormalities for the individual subject and should only continue with Screening and randomisation/treatment if in the investigator's opinion it is safe and appropriate. If there are any unexpected clinically significant findings then the subject should be considered as a screen failure and appropriately investigated/managed.

#### **During follow-up**

If in the opinion of the investigator there are any clinically significant abnormalities (or changes) specific for the individual subject in urinalyses/microscopy, then the subject should be appropriately investigated and managed and this should be recorded as an AE in the eCRF (see Section 6.4.1.3 for further details regarding UTIs).

PAGE 100/139

If there is any suspicion of a symptomatic UTI, laboratory urinalysis/microscopy and urine culture and sensitivity should be sent to the central laboratory (prior to commencing antibiotics, if possible). See Section 6.4.1.3 for further details.

#### Discretionary dipstick urinalysis

Urine dipstick may also be used at the discretion of the investigator when required for a rapid assessment (e.g. if there is a suspicion of a UTI), although laboratory urinalysis/microscopy, and urine culture and sensitivity samples should be sent to the central laboratory for formal confirmation of findings. See Section 6.4.1.3 for managing a symptomatic UTI and Section 6.4.1.4 for the definition of a UTI.

## 8.2.4 Urine Culture and Sensitivity

Fresh urine samples (at least 10 mL) for culture and sensitivity will be collected prior to invasive study procedures to:

- Assist in adapted antibiotic prophylaxis selection (see Section 6.4.1.2) for the procedure;
   or
- If empiric antibiotics are used to cover the procedure, to ensure that a baseline urine culture (prior to the procedure) is available to allow for rapid switching of antibiotics to an appropriate (adapted) antibiotic if the subject develops a symptomatic UTI following the procedure (see Section 6.4.1.3).

During follow-up, if there is any suspicion of a symptomatic UTI, laboratory urinalysis/microscopy and urine culture and sensitivity should be sent to the central laboratory (prior to commencing antibiotics, if possible). See Section 6.4.1.3 for further details.

#### 8.2.5 Pregnancy Test

A urine sample will be collected for a human chorionic gonadotropin pregnancy test as per the schedule in Table 4 and Table 5, for all female subjects of childbearing potential. If this is found to be positive, it will be followed-up with a serum pregnancy test ( $\beta$ -human chorionic gonadotropin).

Any subject becoming pregnant during the study will be withdrawn. All pregnancies that occur during the study are to be reported as described in Section 8.1.5.

#### 8.2.6 Antibody Testing

Blood samples  $(2 \times 6 \text{ mL samples})$  will be collected and serum samples will be sent to the central laboratory for subsequent antibody testing per the schedule in Table 4 and Table 5 for the assay of putative antitoxin-A antibodies.

Batch shipping to specific laboratories in charge of the analyses will be arranged by the central laboratory at appropriate intervals. All samples will be tested for the presence of binding antibodies with a validated assay. Samples found positive for the presence of binding antibodies will be analysed for the presence of neutralizing antibodies using another validated assay. Full details regarding the processing, labelling and shipment processes for these samples are provided in the study manual.

These data will only be provided to the site after the end of the study (database lock).

#### 8.2.7 Other Laboratory Safety Tests

Other laboratory safety tests may be performed at the discretion of the investigator to ensure the safety of the subjects.

PAGE 101/139

#### 8.2.8 Blood Volume to be Collected During the Study

The blood volume collected during the 24-month course of the study depends on the number of treatment cycles received. Assuming 3 mL of blood sampled for each haematology test, 4 mL of blood sampled for each biochemistry test (for serum chemistry), and 12 mL of blood sampled for each antibody test:

- A subject who receives a single study treatment will provide 57 mL of blood
- For each additional treatment cycle, the subject will provide a further 26 mL of blood.

A subject who receives 3 study treatments will therefore provide 109 mL of blood during their study participation.

The maximum amount of blood collected at a single visit is 19 mL (for visits at which samples are collected for all blood tests).

#### 8.3 Physical Examination

Symptom-driven physical examinations will be conducted per the schedule in Table 4 and Table 5, and may also be performed at any other time during the study if clinically indicated.

The first physical examination is conducted at Screening Visit 1. Accordingly, any physical examination abnormalities observed at this visit are to be recorded as medical history, and not as AEs. Any new clinically significant physical examination findings (abnormalities) observed during the study will be reported as AEs. Please see Section 8.1.2.9 and Section 8.1.2.10 regarding neurological AEs, or findings that may represent an MS exacerbation.

Any physical examination findings (abnormalities) persisting at the end of the study will be followed by the investigator until resolution or until reaching a clinically stable endpoint.

#### 8.4 Vital Signs

Vital signs consist of HR, respiratory rate, BP and body temperature:

- HR, respiratory rate and BP should be measured in the sitting or supine position, but must be performed consistently throughout the study
- Body temperature should be measured using a consistent method throughout the study (oral or tympanic is preferred).

#### Screening Visit 1

Body weight and height will also be measured as part of the vital sign assessment at Screening Visit 1 only.

#### Treatment and Retreatment Visits

During the Treatment and Retreatment Visits vital signs must be measured:

- Prior to treatment administration; and
- Approximately 30 minutes after completion of treatment administration.

PAGE 102/139

#### 9 STATISTICS

## 9.1 Analysis Populations

The following populations will be used during statistical analyses:

- Screened population: All subjects screened (i.e. who signed the informed consent)
- **Safety population:** All subjects who received at least one IMP administration (including only partial administration) of the IMP. Subjects will be analysed as treated (actual treatment)
- **Modified intention to treat (mITT) population:** All randomised subjects who received at least one IMP administration. Subjects will be analysed as randomised (planned treatment)
- **Per protocol (PP) population:** All subjects in the mITT population who have no impacting major protocol deviations (i.e. that could potentially affect the primary efficacy endpoint outcome for the subject) as described in the protocol deviations document. Subjects will be analysed as randomised.
- **Urodynamic population:** All subjects in the mITT population included in the urodynamic subset at randomisation.

The following protocol deviations will impact the PP population (for further details of protocol deviations see Sections 9.1.2 and 11.1.2):

- 1) Subject does not receive the full first administration of the IMP
- 2) Subject does not have a valid (nonmissing) UI data point at the Week 6 Visit following the first administration of the IMP.

#### 9.1.1 Populations Analysed

The primary analysis based on the primary efficacy endpoint will be performed on the mITT population. In addition, a supportive analysis will be conducted on the PP population.

The analyses of safety data will be performed based on the safety population.

The analyses of urodynamic parameters will be performed on the urodynamic population.

## 9.1.2 Subject Allocation and Reasons for Exclusion from the Analyses

Any major protocol deviation (see Section 11.1.2 for definition) will be described in the Protocol Deviation Document and its impact on inclusion in each analysis population (mITT, PP and safety populations) for any subject will be specified. The final list of protocol deviations impacting the safety, mITT and PP populations will be reviewed prior to database lock, before any unblinding of treatment groups. The list may be updated up to the database lock to include any additional major protocol deviations impacting inclusion in the PP population.

## 9.2 Sample Size Determination

The sample size is based on the ability to detect a statistically significant treatment difference in the weekly number of UI episodes at Week 6 following treatment in the two Dysport® arms compared to the placebo arm.

Assuming a decrease of 21 UI episodes per week in each Dysport® arm and a decrease of 12 UI episodes per week in the placebo arm, with a common standard deviation of 20 UI episodes, 80% power, and an alpha of 0.025 (as testing of both the 600 U and 800 U doses vs. the placebo

PAGE 103/139

dose will be performed simultaneously), a sample size of N=96 subjects per dose group for the primary analysis (a total of 288 subjects) is needed.

Assuming a treatment group random allocation ratio 1:1:1, a sample size of 106 subjects in each treatment group will have 80% power to detect a difference in UI of 9 episodes (the difference between UI in Dysport® 600 U and Dysport® 800 U groups and in placebo group assuming a common standard deviation equal to 20 episodes and a dropout rate equal to 10% with a 0.025 two-sided type one error rate. A total of 318 subjects would therefore need to be enrolled.

However, in order to ensure that the development program will deliver adequate Dysport exposure data to meet ICH E1 guideline recommendations, a total of 330 subjects are planned to be randomised.

#### 9.3 Significance Testing and Estimations

All statistical tests will be performed two-sided with a type one error rate set at 5%.

Experiment-wise control of type one error for the primary endpoint will be performed using a conservative approach. The primary efficacy hypotheses are as follows:

- (1) Ho: There is **no** difference between treatment with 600 U or 800 U Dysport® and treatment with placebo with respect to the change from pretreatment to Week 6 after the first study treatment in the number of UI episodes per week.
- (2) Ha: There **is** a difference between treatment with 600 U or 800 U Dysport® and treatment with placebo with respect to the change from pretreatment to Week 6 after the first study treatment in the number of UI episodes per week.

For the primary endpoint, due to multiple comparisons of more than two treatments, a Hochberg correction will be applied to control the global type one error at 5% significance level. If both p-values for the two primary tests (the test of 800 U vs. placebo and the test of 600 U vs. placebo) are lower than 0.05, both will be declared statistically significant. If one of the primary tests has a p-value greater or equal to 0.05, then the other test will be declared statistically significant if its p-value is lower than 0.025 (and thus half of the overall experiment wise alpha of 0.05).

The two ordered secondary endpoints will be tested for both doses at the 0.05 level (using a hierarchical methodology) if, for both doses, the two primary tests achieve a p-value lower than 0.05. If one of the primary tests has a p-value greater or equal to 0.05, and the other has a p-value lower than 0.025, secondary endpoints will be assessed (using hierarchical methodology) for the dose group with p-value lower than 0.025, at the 0.025 significance level.

In order to control the family-wise type one error, the following hierarchical testing procedure will be applied for the testing of the superiority of both Dysport® doses to placebo for the primary and selected secondary endpoints (ordered as described in Section 3.2.2.2):

- Step 1: The 800 U Dysport® and 600 U Dysport® doses will be compared to placebo on the primary endpoint. If the p-values associated with both doses are <0.05 then both doses will be declared statistically significant and the testing will proceed at the 0.05 level from step 2 onwards. If one dose has  $p\ge0.05$  but the other has p<0.025 (significant dose) then testing will proceed at the 0.025 level from step 2 onwards on the significant dose only. If both dose groups have  $p\ge0.05$  or one dose group has  $p\ge0.05$  and the other dose group has  $p\ge0.025$ , the testing procedure will be stopped
- Step 2: The 800 U Dysport® and 600 U Dysport® doses will be compared to placebo for the first secondary endpoint. Testing will be at the significance level defined in step 1 (0.05 or 0.025). If the p-value associated with this test is lower than the significance level

PAGE 104/139

defined in step 1 then it will be considered significant and testing will proceed to step 3. Otherwise the testing procedure will be stopped

• Step 3: The 800 U Dysport® and 600 U Dysport® doses will be compared to placebo for the second secondary endpoint. Testing will be at the significance level defined in step 2 (0.05 or 0.025). If the p-value associated with this test is lower than the significance level defined in step 2 then it will be considered significant.

The above testing rules ensure that the hierarchical procedure controls the experiment-wise type one error (i.e. over the three tests) at the 0.05 level for relevant secondary endpoints.

In the event the hierarchical testing procedure is stopped at the end of any particular step, the testing of the following steps will be considered descriptive only and no formal statistical conclusion will be drawn.

Each other secondary endpoint not included within the hierarchical testing procedure will be analysed for exploratory purposes only to compare each Dysport® dose to placebo at a 0.05 type one error rate.

#### 9.4 Statistical/Analytical Methods

Statistical analyses will be performed by an external CRO, managed by the sponsor's Biometry Department.

A SAP describing the planned statistical analysis in detail will be developed as a separate document.

Statistical evaluation will be performed using Statistical Analysis System® (version 9.1 or higher).

#### 9.4.1 Demographic and Other Baseline Characteristics

In order to ensure balance of treatment groups, descriptive summary statistics (number of patients, mean, standard deviation, standard error mean, 95% confidence interval, median, minimum, maximum) or frequency counts of demographic and baseline data (medical history, pre-existing conditions and ongoing medical history, prior medications/therapies etc.) will be presented by treatment group and overall for the mITT and urodynamic populations.

Unless prohibited by local regulation, race and ethnicity are collected to ensure data robustness for safety and efficacy evaluation, and to prevent adverse reactions or improve benefits in the target population.

#### 9.4.2 Homogeneity of Treatment Groups

In order to assess the homogeneity of treatment groups at Baseline, 95% confidence intervals will be provided to detect any clinical nonhomogeneity.

#### 9.4.3 Data Imputation

No imputation is planned for the primary analysis of the primary endpoint. For sensitivity analyses, imputation will be performed using a multiple imputation approach for handling missing data on the mITT population.

#### 9.4.4 Subject Disposition and Withdrawals

The numbers and percentages of subjects enrolled and included in the analysis populations mentioned in Section 9.1.1 will be tabulated by country and site. The reasons for subject exclusions from each of the populations will also be tabulated. In addition, the numbers of subjects who were randomised, treated, prematurely discontinued and completed at each of the study periods (e.g. double blind treatment period, active follow-up period) will be tabulated by

PAGE 105/139

treatment group (600 U, 800 U, placebo for Treatment 1; 600 U, 800 U for subsequent treatments). Primary reasons for discontinuation of study treatment will be tabulated.

#### 9.4.5 Efficacy Evaluation

As indicated in Section 7.1, the primary efficacy variable is the change in the weekly number of UI episodes from Baseline (Day 1) to Week 6 after the first treatment.

Secondary efficacy variables are:

- weekly number of UI episodes
- proportion of subjects with no episodes of UI
- I-QoL total summary score (as well as individual domain scores i.e. avoidance and limiting behaviour, psychosocial impact, and social embarrassment)
- urinary frequency (total, spontaneous only, CIC only)
- 24-hour voided volume (total, spontaneous only, CIC only)
- volume per void (total, spontaneous only, CIC only)
- EQ-5D-5L score
- mPGI-I score
- proportion of subjects with UI response at several levels (i.e. ≥30% improvement, ≥50% improvement, ≥75% improvement, etc.)
- time to retreatment request
- time to eligibility for retreatment
- time between treatments.

Efficacy assessments performed only in the urodynamic population are described in Section 9.6.

Full details of these assessments and timings are given in Section 7.2.

The study Baseline value will be defined as the last value available prior to the first study IMP treatment administration.

The aetiology of NDO (SCI or MS) and prior intradetrusor BTX-A usage for UI (BTX-naive and BTX-non-naive) will be used as covariates in the primary model. The results of the treatment effect will be presented for each subgroup formed by the covariates (see Section 9.5 for further details). In order to assess the impact of missing data on the conclusion of the primary analysis, a sensitivity analysis of the primary efficacy endpoint will be performed using a multiple imputation approach.

If the parametric assumptions of the analysis are not satisfied, then a suitable transformation or a nonparametric procedure will be sought.

Secondary efficacy endpoints will be assessed according to their scale (categorical or continuous), using a logistic regression model, mixed model, or survival analysis-type methods (e.g. Kaplan-Meier plots, log-rank statistics).

Time to event data will be analysed by using survival methods. The results will be presented both in summary tables and graphically in Kaplan-Meier plots.

Responders defined as subjects having an improvement in UI will be presented at several levels (i.e.  $\geq$ 30% of improvement,  $\geq$ 50% of improvement,  $\geq$ 75% of improvement, etc.) for exploratory purposes.

PAGE 106/139

#### 9.4.6 Adjustment for Country/Site Effect

No stratification for country/site is to be performed, and no adjustment for country or site effect is planned.

#### 9.4.7 Safety Evaluation

All safety data will be included in the subject data listings. Analyses and summary tables will be based upon the safety population.

All AEs will be coded according to the Medical Dictionary for Regulatory Activities (MedDRA) (current version at the time of database lock), and will be classified by MedDRA preferred term and system organ class. AE listings will be presented by subject, system organ class and preferred term.

Incidence of all reported AEs/treatment emergent AEs, AESIs, and SAEs will be tabulated by treatment group (600 U, 800 U, placebo for Treatment 1 and 600 U, 800 U for subsequent treatment(s)) and overall. In addition, summary tables will be presented by maximum intensity, drug relationship and AEs associated with premature withdrawal of IMP.

A treatment emergent AE is defined as any AE that occurs during the active phase of the study if:

- It was not present prior to receiving the first dose of IMP; or
- It was present prior to receiving the first dose of IMP but the intensity increased at any point in the study following the first dose of IMP.

Concomitant medication will be coded by using World Health Organisation Drug Dictionary (WHODRUG; current version at the time of database lock) and will be summarised by treatment group (600 U, 800 U, placebo for Treatment 1 and 600 U, 800 U for subsequent treatment(s)) and overall, with the number and percentage of subjects receiving concomitant medication by drug class and preferred drug name.

Summary statistics (mean, median, standard deviation, standard error mean, and range as appropriate) by treatment group and overall will be presented for vital signs, laboratory safety tests, laboratory urinalysis/microscopy etc. at each assessment with change from Baseline. For laboratory safety data, abnormal values will be flagged in the data listings and a list of clinically significant abnormal values will be presented. Shift tables from Baseline of the number and percentage of subjects with low, normal or high values and normal or abnormal examinations will be presented by treatment group (600 U, 800 U, placebo for Treatment 1 and 600 U, 800 U for subsequent treatment(s)).

#### 9.4.8 Antibody Testing

The number and percentage of subjects with the presence of neutralising BTX-A antibodies at Baseline will be described. The number of seroconverters (subjects having a negative result at Baseline and at least one positive result at one post-treatment timepoint) for neutralising antibodies will be reported for each treatment group.

### 9.5 Subgroup Analyses

Descriptive statistics for the primary and selected secondary endpoints (to be defined in the SAP) will be provided for the mITT population within each category of the randomisation stratification variables: aetiology of NDO (SCI or MS) and also BTX-A bladder naive and BTX-A bladder non-naive). Additional subgroup analyses will be planned according to clinical interest and detailed in the SAP.

Subjects will also be categorised as follows:

PAGE 107/139

- (1) No previous BTX-A treatment at any anatomical location
- (2) No previous intradetrusor BTX-A usage for UI but with previous BTX-A treatment at any other anatomical location
- (3) Previous intradetrusor BTX-A usage for UI, with or without previous BTX-A treatment of any other anatomical location (stratified according to this category).

## 9.6 Urodynamics Subset

At least 200 subjects will be included in the urodynamics subset. The analysis of MCC (representative urodynamic parameter) will reach a power of 90% with an alpha of 0.05, if the treatment groups are well-balanced, using the assumptions described in Table 21.

Table 21 Estimate of minimum delta required for MCC (example urodynamic parameter)

	Change from Baseline to Week 6 following first treatment in placebo group [= a]	Change from Baseline to Week 6 following first treatment in Dysport group [= b]	Common standard deviation	Minimum delta to reach 200 subjects with 90% power and an alpha 0.05 [= b-a]
MCC (mL)	15.5	120	212.9	104.5

MCC=maximum cystometric capacity.

Urodynamic secondary endpoints will be evaluated using a hierarchical analysis for the following ordered parameters:

- MCC
- MDP during storage
- Vol@1stIDC
- Proportion of subjects with no IDCs on urodynamic assessment

The full hierarchical methodology will be detailed in the statistical analysis plan.

All other secondary endpoints related to urodynamics will be presented for exploratory purposes.

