7.6.6 Other Analysis of Secondary Efficacy Endpoints

The analysis of efficacy of the above-mentioned endpoints (primary endpoint and secondary endpoints included in the hierarchical analysis) will be conducted at timepoints other than Week 6 in the DBPC Cycle and is described below (except urodynamic endpoints as only performed at Week 6). The analysis of other secondary endpoints (see Section 3.2) is also described below.

Descriptive summaries will be performed for the DBPC Cycle and by Dysport Cycles (i.e. Dysport Cycle 1, Dysport cycle 2 ...), see the schematic diagram in Section 7.1.

Statistical comparison analyses are only applicable for the DBPC treatment cycle. Analyses between treatment groups, Dysport 600 U vs. Placebo, and Dysport 800 U vs. Placebo will be performed accordingly using GLMM and MMRM as mentioned below for each endpoint. As all subjects should have visits up to and including week 12, but thereafter visits are dependent on whether the subject receives retreatment, statistical testing between treatment groups will be performed only up to Week 12, inclusive. All secondary endpoints not included in the hierarchical analysis are considered as exploratory endpoints and will therefore be analysed for exploratory purposes only to compare each Dysport dose to placebo, alpha at 0.05 level.

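### The 90% power quoted for MCC in the urodynamic subset fits pooled Dysport against placebo; each planned dose comparison has about 80%

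*Protocol*

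**What the plan says.** Protocol 9.6 sets the subset size, "At least 200 subjects will be included in the urodynamics subset", and then states: "The analysis of MCC (representative urodynamic parameter) will reach a power of 90% with an alpha of 0.05, if the treatment groups are well-balanced". Table 21 gives the inputs: mean change of 15.5 mL on placebo and 120 mL in one Dysport group, a common standard deviation of 212.9 mL and a difference of 104.5 mL. The last column is headed "Minimum delta to reach 200 subjects with 90% power and an alpha 0.05". Neither the text nor the table says which comparison the 90% refers to.

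Other sections fix the remaining terms:

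- **Sidedness.** Protocol 9.3 makes all tests two-sided at 5%.
- **Allocation.** Protocol 3.3.1 keeps the 2:2:1:1 sequence ratio within the urodynamic subset and combines the two placebo sequences for Treatment 1. The three Treatment 1 arms are therefore equal in size.
- **Tests.** SAP 7.6.6 says: "Analyses between treatment groups, Dysport 600 U vs. Placebo, and Dysport 800 U vs. Placebo will be performed accordingly", each at 0.05. SAP 7.6.6.2 analyses the urodynamic changes with the ANCOVA of SAP 7.6.4.2, which is set up for those same two pairwise tests.
- **Pooled doses.** SAP 7.1 lists All Dysport as a display group. No test of pooled Dysport against placebo is described.

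**The concern.** Table 21 has one Dysport column, but the trial has two Dysport arms and tests each against placebo. A power figure for 200 subjects in two groups cannot be carried over to comparisons that each use only two of three arms, about 134 of the 200 subjects.

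This is the only power justification shown for the subset, and Protocol 9.6 puts MCC first in an ordered list of urodynamic endpoints. A reader will take 90% as the power of each MCC test. If one dose then misses significance, the result would be judged against a power that the test never had. The calculation also makes no allowance for missing Week 6 data, whereas the primary calculation in Protocol 9.2 assumes 10% dropout to the same visit.

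**Working it through.** **Inputs.** Difference 120 − 15.5 = 104.5 mL, SD 212.9 mL, total 200 (Protocol 9.6, Table 21); two-sided alpha 0.05 (Protocol 9.3); equal arms at Treatment 1 (Protocol 3.3.1), so 200/3 ≈ 66.7 per arm. The standardised difference is 104.5/212.9 = 0.491.

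**Formula.** For groups of n1 and n2, SE = SD × √(1/n1 + 1/n2). The normal approximation to power is Φ(difference/SE − 1.960). The non-central t figures use whole numbers of subjects.

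**Step 1: reproduce the stated 90%.** Pool the two doses, 133.3 against 66.7:

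- SE = 212.9 × √0.0225 = 31.94 mL; 104.5/31.94 = 3.272.
- Power = Φ(3.272 − 1.960) = Φ(1.312) = 90.5%. The non-central t at 133 against 67 gives 90.3%.
- Smallest difference for 90% power: (1.960 + 1.282) × 31.94 = 103.5 mL, or 103.9 mL with the t distribution. Table 21 has 104.5 mL.
- Total needed for 90% at 2:1: 198 (normal) or 201 (t). The protocol has 200.

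The pooled contrast therefore matches the power, the total and the difference.

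**Step 2: the planned comparison.** One dose against placebo, 66.7 against 66.7:

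- SE = 212.9 × √0.03 = 36.88 mL; 104.5/36.88 = 2.834.
- Power = Φ(2.834 − 1.960) = Φ(0.874) = 80.9%. The non-central t at 67 against 67 gives 80.5%.
- Smallest difference for 90% power: (1.960 + 1.282) × 36.88 = 119.5 mL, or 120.1 mL with the t distribution.
- Size needed for 90% at 104.5 mL: 2 × (1.960 + 1.282)² × (212.9/104.5)² = 87.2, so 88 per arm (normal) or 89 (t). That is 3 × 88 = 264 to 3 × 89 = 267 subjects.

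**Step 3: 10% loss by Week 6** (borrowed from the primary calculation; none is stated for the subset). This leaves 60 per arm:

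- SE = 212.9 × √(2/60) = 38.87 mL; 104.5/38.87 = 2.688.
- Power = Φ(0.728) = 76.7%. The non-central t gives 76.0%.

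**Summary (non-central t, two-sided 0.05, 104.5 mL)**

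| Comparison | Group sizes | Power |
|---|---|---|
| Pooled Dysport vs placebo (not planned) | 133 vs 67 | 90.3% |
| Two equal groups (not this design) | 100 vs 100 | 93.2% |
| One dose vs placebo (planned) | 67 vs 67 | 80.5% |
| One dose vs placebo, 10% loss | 60 vs 60 | 76.0% |

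The primary calculation, by contrast, is done per dose: 96 per group, a difference of 9, SD 20 and alpha 0.025 give 80.4%, in line with the stated 80%.

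**The case against.** Four points can be made for the plan as written.

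**Protocol 9.6 does not say that the figure is pooled.** That is so; the pooled reading is inferred from the numbers. Another reading also comes near 90%: the chance that at least one dose is significant at an unadjusted 0.05 is about 91.8%. The documents never define power that way, and the pooled reading fits the total and the difference more closely. On either reading, power per dose stays at about 80%, and power for both doses together is about 70%.

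**The planned model is an ANCOVA.** Protocol 9.6 does not say whether 212.9 mL is a raw or a residual standard deviation. If it is raw, covariates could raise power: explaining 10% of the variance gives about 84% per dose at 67 per arm, and about 24 to 25% is needed to reach 90%. The documents give no correlation, so this gain cannot be claimed. It does mean that the 80% should be labelled as unadjusted.

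**200 is a minimum.** A larger subset would have more power per dose: about 84% at 220, 87% at 240 and 90% at 267. But Table 21 ties its 90% to 200 subjects.

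**MCC is secondary.** The SAP treats endpoints outside its two-item hierarchy as exploratory. This stands and limits the weight of the point: the primary sample size and the type one error control are untouched.

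**Conclusion.** The concern holds. At 200 balanced subjects, the 90% is not the power of either planned MCC comparison. Each dose against placebo has about 80% power (80.5%), or about 76% with 10% missing at Week 6. The chance of missing the assumed 104.5 mL effect is 19.5% per dose rather than 10%.

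This rests on equal arms in the subset, two-sided alpha of 0.05 per dose as SAP 7.6.6 sets it, and 212.9 mL as the standard deviation with no covariate gain. The 10% loss is an assumption carried over from the primary endpoint. The arithmetic behind the 90% is sound for pooled Dysport; what is wrong is attaching it to an analysis that compares the doses separately. It should be corrected, but it does not threaten the primary result.

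**What to change.** Restate Protocol 9.6 and Table 21 to name the comparison and give its power. With 200 subjects balanced over three arms and no covariate adjustment, each dose-versus-placebo comparison of MCC has about 80% power for 104.5 mL at two-sided 0.05, and about 76% if 10% have no Week 6 measurement. A difference of about 120 mL is needed for 90%. If the 90% is kept, label it as the power for pooled Dysport against placebo and say that this contrast is not a planned test. If any gain from baseline adjustment is to be claimed, state the assumed correlation.

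The cost is a change of wording and a less favourable stated power. It needs no extra patients or procedures and no change to the planned tests. Enlarging the subset to about 267 subjects would give 90% per dose, but the correction does not require it.
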